#### **Enrollment procedures**

The following events will occur in order:

- 1. Screening for eligible patients
- 2. Informed consent
- 3. Randomization

- 4. Administration of study drug starting the morning of surgery and for 2 additional mornings
- 5. Collection of data
- 6. Completion of CRF information

The treatment periods extends from the morning of surgery until the earlier of POD 2 or hospital discharge. Study personnel will follow the study subject until the earlier of POD 2 or hospital discharge. In the case of an adverse event, the study subject will be followed until the resolution of the event.

#### Handling incorrect randomization

Any event where a subject receives the incorrect treatment or is assigned to the incorrect group will be recorded and judged as an unanticipated problem or protocol deviation at the discretion of the principal investigator.

#### F. Measurements

Data will be recorded on a case report form (CRF) which will be available electronically and on paper format.

Demographic data to be obtained includes height (cm), weight (kg), age (yr), gender, physical status (ASA), and self-declared ethnicity. Patients will be questioned for social history (tobacco) and medical history (pulmonary disease, kidney disease, diabetes mellitus, neurological disease, chronic pain conditions, illegal drug usage, alcohol abuse, myocardial infarction, previous surgery or stent placement and medications usage). Available preoperative laboratory tests and medication list will be recorded. Individual risk for nausea and vomiting will be determined using the Apfel score.

Data obtained from electronic medical records will include: operation time, surgery type, intraoperative opioid consumption, postoperative opioid consumption in PACU and in ward,

breakthrough pain medication requirements, pain scores in PACU and ward, requirement of oxygen in PACU and ward, nausea and vomiting, requirement of antiemetics, pruritus, requirement of antihistaminic medications, ambulation time, flatus, ileus, bowel movements, constipation, length of stay and any side effects or complications. Preoperative and postoperative laboratory data including but not limited to liver function and coagulations test results will also be collected from electronic medical records. Patient functionality will also be recorded including bathing, toileting, walking and moving.

The Residual volume will be measured within 30 minutes after urination using the batterypowered, portable Bladder scan™ BVI 3000® (Verathon, Bothell, WA, USA). The scanner will be placed on the suprapubic area and held stationary during measurement scanning. The diameter of the bladder and volume of urine will be calculated from the scan data. Scans will be repeated several times to ensure accuracy in measurements. The average of the measurements at each measurement time will be analyzed. All clinical procedures will be performed by trained MD research fellows in the ward twice daily. Surgical team will be blinded to volume determined by scanning and we will also record if they had ordered indwelling catheterization.

We will use Myles QoR scale to formally evaluate quality of recovery on 2 or day of discharge (whichever comes earlier). Myles QoR scale is a validated scoring system allows quantification of patient's early postoperative health status, which is also a description of quality of recovery[32]

ORSDS is 4-point scale that evaluates 3 symptom distress dimensions (frequency, severity, bothersomeness for 12 opioid related side effects[53]. ORSDS questionnaire will be administered by a trained research fellow on first and second postoperative days/day of discharge (whichever comes earlier)

Patient satisfaction with their recovery will be questioned before discharge using a 0-100 scale (where 0 indicates no satisfaction and 100 indicates complete satisfaction).

Adverse events and serious adverse events occurring at any time during the study period will be recorded on a specific form in the CRF.

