#### A. Primary Aim

To assess whether patients who received Naloxegol have a lower volume of residual urine in bladder.

Hypothesis: Our primary hypothesis is that patients who received Naloxegol 25 mg given once in the morning every day will have lower volume of residual urine in bladder when compared to placebo.

Post-void residual volume will be measured after asking patient to urinate independent of their previous urination. Post-void residual is a measurement of the urine that remains in the bladder less than 30 minutes following voiding that identifies urinary retention.

Ultrasound has been used as an imaging modality to evaluate bladder function, and its use in the perioperative period as a diagnostic tool for POUR has gained popularity in the past decade. Several studies have shown good correlation between the volumes measured by bladder catheterization and by ultrasound.

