In the PACU and postoperative periods, patients will be managed at the discretion of the primary care team and the staff anesthesiologist. The need for straight catheterization in PACU and/or on the floor when it is medically indicated (volumes exceeding 400 ml) will be recorded by the study team and subsequent bladder scan will therefore not be done. Postoperatively, all patients will be given intravenous or oral opioids for pain control. Clinicians will adjust analgesic management as necessary in an effort to adjust verbal response pain scores to less than 4.

Clinical evaluators for the outcomes will be blinded to group allocation and Pharmacy personnel not involved in evaluations will prepare the study drugs. Clinicians including nurses will be blinded to monitoring and will be required to perform their standard of care management after surgery.

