#### Primary analysis.

We will test the primary hypothesis that subjects who received Naloxegol 25 mg given once in the morning every day will have lower volume of residual urine in bladder when compared to placebo. We will compare the randomized groups on the volume of residual urine in bladder, which will be measured twice per day for up to 3 days (i.e., a maximum of 6 measurement times in total), using a linear mixed model adjusting for the within-subject correlation (using an autoregressive correlation structure). At each measurement time, the average of the measurements will be analyzed. Any imbalanced baseline characteristics and volume of residual urine in bladder prior to the procedure will be included as covariates in the model. If the group-by-time interaction is non-significant (P > 0.20), we will assess the group difference on the volume of residual urine across over all the measurements. In the presence of a group-by-time interaction, the group difference will be assessed separately at each measurement time and a Bonferroni correction will be made for multiple comparisons to maintain the hypothesis-wise 2-sided type I error at 0.05 (the significance criterion will be 0.05 / 6).

Second, we will assess the treatment effect within chronic opioid users and nonusers using the same statistical methods as above. The significance level will be 0.025 for each of the two subgroup analyses (Bonferroni correction).

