#### Secondary and exploratory analysis.

We will test the following three secondary hypotheses: subjects who received Naloxegol 25 mg given once in the morning every day will have (1) fewer opioid-related side effects, (2) less need of indwelling catheterization determined by the residual volume to be above 400 ml, and (3) improved quality of recovery as compared to placebo.

The two groups will be compared on the incidence of any opioid-related side effects using a logistic regression. The frequency, severity, and bothersomeness for each of the 12 opioid-related side effects on POD 1 and 2 will be summarized. We will compare the two groups on incidence (any versus none) of need for indwelling urinary catheterization (defined as residual urine volume > 400 ml) using logistic regression. The two groups will also be compared on the Quality of Recovery scale measured on POD 2 (or day of discharge if it occurs earlier) using a linear mixed model with an autoregressive correlation structure. All the analyses will be adjusted for imbalanced baseline characteristics, if any. The hypothesis-wise 2-sided type I error for each of the secondary outcome will be controlled at 0.017 (i.e., 0.05/3, Bonferroni correction).

In addition, we will summarize the following exploratory outcomes, including satisfactory of the quality of recovery (a subjective 100-point scale) and length of hospital stay after surgery.

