#### H. Sample Size Considerations

The sample size consideration was based on the test for the primary hypothesis that patients who received Naloxegol 25 mg given once in the morning every day will have lower volume of residual urine in bladder when compared to placebo. We would need 62 patients per group [56] to have 90% power at a 2-sided alpha level of 0.05 to detect an effect size of 0.4 or more. The effect size estimation of 0.4 was very conservative as compared to the mean difference of 120 ml (SD: approximate 60 ml) in the volume of residual urine observed by Jose Carlos, I. T., et al [57]. The effect size is the difference in means of the two randomized groups divided by the pooled standard deviation. A maximum of six measurements are planned, twice per day for 3 days. However, we assumed 4 measurements per patients with a correlation of 0.3 to be conservative for the sample size calculation. Considering a loss of follow-up rate of 10%, we will need 12 more patients to reach the planned power with an end sample size of 136. A blinded data quality check will be conducted at 50% (68 patients) of the planned enrollment of 136 patients. In addition to the 136 patients, we will enroll 2 pilot patients to test feasibility of recruitment, protocol adherence, randomization process, and data collection.

SAS software version 9.4 for Windows (SAS Institute, Cary, NC) will be used for all statistical analyses and graphics.

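### The plan gives two different triggers for the primary-outcome scan, so the highest residual volumes may go unrecorded when a patient cannot void or is catheterized

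*Combined protocol and SAP*

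**What the plan says.** Three statements describe when the primary volume is measured.

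- Section A (Primary Aim), first statement: "Post-void residual volume will be measured after asking patient to urinate independent of their previous urination". The trigger is a request.
- Section A, next sentence: "Post-void residual is a measurement of the urine that remains in the bladder less than 30 minutes following voiding". The trigger is a void.
- Section F (Measurements): "The Residual volume will be measured within 30 minutes after urination". The trigger is again a void.

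Section E (Protocol) adds a rule for patients who need straight catheterization in the PACU or on the ward for volumes above 400 ml. That need "will be recorded by the study team and subsequent bladder scan will therefore not be done". What is recorded is the need; the section does not say that the volume behind it enters the primary data.

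The primary analysis in Section G compares up to six volumes per patient "using a linear mixed model adjusting for the within-subject correlation (using an autoregressive correlation structure"). It has no rule for a failed void, a catheterized patient or a missing scan, and no sensitivity analysis for any of them. A secondary outcome uses the same volumes: "need for indwelling urinary catheterization (defined as residual urine volume > 400 ml").

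Section H plans for "90% power at a 2-sided alpha level of 0.05 to detect an effect size of 0.4 or more", with 62 patients per group and a 10% allowance for loss to follow-up.

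**The concern.** The three statements agree for a patient who voids. They part for a patient who is asked to void and cannot. The request-based statement gives a scan, probably with a large volume. The two void-based statements give no qualifying scan. Staff working from Section F could skip that scan and still be following the protocol.

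A scan skipped for this reason is missing because of the value it would have shown. A likelihood-based mixed model handles missing values that can be predicted from recorded ones. It does not correct for values that are missing because they themselves are high. If naloxegol lowers residual volume, more high values are lost on placebo than on naloxegol, and the estimated difference shrinks. With no true effect, the same loss falls on both arms, so the harm is to the effect estimate and power rather than to the type I error.

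The catheterization rule in Section E adds to the problem. Patients with the highest volumes are the likeliest to be catheterized, and their next scan is not done. The secondary outcome is exposed too, because a volume above 400 ml that is never scanned cannot be counted as an event.

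**Working it through.** **1. The plan's own sample size.** Inputs from Section H: effect 0.4 SD, two-sided alpha 0.05, power 90%, m = 4 measurements, correlation 0.3. I take the correlation as exchangeable.

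- Variance factor for the patient mean: (1 + 3 × 0.3) / 4 = 0.475.
- n per group = 2 × (1.960 + 1.282)² / 0.4² × 0.475 = 62.4, against the stated 62. Power at 62 per group is 89.8%.
- Total: 124 × 1.10 = 136.4, against the stated 136.

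The figure reproduces. It allows for 10% loss to follow-up, but not for scans lost because the volume is high.

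**2. Effect if the high scans are not recorded.** The documents give no rate of failed voids at a scan, so I assume that the highest 5%, 10% or 20% of placebo volumes are lost, and that the same volume threshold applies on naloxegol. In SD units, placebo is N(0, 1) and naloxegol N(−0.4, 1). The mean of what remains below threshold c is −φ(c)/Φ(c) on placebo and −0.4 − φ(c + 0.4)/Φ(c + 0.4) on naloxegol.

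| Placebo scans lost | c | Placebo mean | Naloxegol mean | Difference | Naloxegol scans lost |
|---|---|---|---|---|---|
| 5% | 1.645 | −0.109 | −0.450 | 0.34 | 2.0% |
| 10% | 1.282 | −0.195 | −0.502 | 0.31 | 4.6% |
| 20% | 0.842 | −0.350 | −0.607 | 0.26 | 10.7% |

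**3. The same question through a repeated-measures model.** The closed form ignores correlation between scans, so a simulation was run: 62 per group, four scans, correlation 0.3, true difference 0.40 SD, likelihood-based model with exchangeable correlation, 800 runs per setting. Each cell gives the mean estimated difference in SD, then power. With nothing lost, the difference was about 0.40 and power about 90%.

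| Placebo scans above threshold | (a) Only the high scan is lost | (b) High scan recorded, all later scans skipped | (c) High scan and all later scans lost |
|---|---|---|---|
| 5% | 0.35; 86% | 0.40; 88% | 0.33; 81% |
| 10% | 0.31; 84% | 0.40; 88% | 0.30; 77% |
| 20% | 0.26; 76% | 0.40; 85% | 0.24; 63% |

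Column (a) agrees with step 2. The contrast between (b) and (c) matters most: skipping later scans costs some power but almost no bias, provided that the high volume itself is in the data.

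**4. Patients or scans?** In (a), 0% to 1.5% of placebo patients have no scan at all; the others stay in the model through their remaining scans. In (c), the figures are 5%, 10% and 20% on placebo and 2%, 5% and 11% on naloxegol.

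**The case against.** The best defence is that Section A already gives the working instruction: ask the patient to urinate, then scan. Section F then only adds a time limit to that procedure. No section says that a patient who cannot void goes unscanned. If staff work this way, the high volumes are recorded and the bias largely disappears, as column (b) shows. That reading is available, but two of the three statements name a void as the trigger, one of them in the section that sets out how measurements are made. A primary outcome should not depend on which sentence the assessor follows.

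Three stronger readings are tempting, and the documents do not support them.

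- A reader might infer that patients in retention have no measurement. Section A can be read to allow the scan, so the loss is possible rather than stated.
- A reader might infer that these patients leave the primary analysis. The mixed model keeps anyone with at least one scan, so scans are at risk, not necessarily patients.
- A reader might put the loss in millilitres: 0.4 × 60 ml = 24 ml as the planned effect, and 5 percentage points × an assumed 400 ml gap = 20 ml lost. Section H plans in SD units, and the 60 ml comes from a cited study. The inputs also clash. With 5% of placebo patients 400 ml above the rest and none on naloxegol, placebo variance is 60² + 0.05 × 0.95 × 400² = 11,200, the pooled SD is √((3,600 + 11,200)/2) ≈ 86 ml, and 0.4 SD is about 34 ml.

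Nor is the 5–70% incidence of retention in the introduction a rate of failed voids here. It is a general range, and this trial excludes conditions and medications that cause retention.

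**Conclusion.** The point holds as a conflict in the definition of the primary outcome, with a real but conditional risk of bias toward no difference. Following Section F literally would lose 12% to 35% of the planned effect (0.40 to between 0.35 and 0.26 SD) and take power from about 90% to between 86% and 76%. If later scans are lost as well, power could fall to between 81% and 63%.

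These sizes rest on the assumed 5% to 20% of placebo scans, normally distributed volumes, a sharp threshold, and an exchangeable correlation where the plan specifies an autoregressive one. The direction depends less on them: high values that go unrecorded attenuate a true difference. The catheterization rule alone does little harm to the estimate if the volume before catheterization is recorded, but the plan does not say that it will be. This should be corrected; it does not undermine the sample size calculation.

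**What to change.** - Use one definition in Section A (Primary Aim), Section F (Measurements) and the primary analysis in Section G: bladder volume scanned within 30 minutes after the patient is asked to void, whether or not urine is passed.
- Add a field to the CRF at each scan for voided or did not void, and include all these volumes in the primary analysis.
- Record any bladder volume measured before a catheterization, and state whether and how it enters the primary analysis.
- State how later time points are analysed in catheterized patients, and apply the same rule to the secondary outcome of a residual above 400 ml.
- Pre-specify a sensitivity analysis that ranks catheterized patients worst, for example a rank-based or composite comparison.

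The cost is a few sentences, one CRF field, a little more analysis, and possibly a few scans within the planned schedule that would otherwise have been skipped. Clinical care does not change.

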#### G. Data Analysis

Naloxegol group and placebo group will be compared for balance of baseline characteristics using standard descriptive statistics (i.e., mean  $\pm$  standard deviation, median [Q1, Q3], or N (%) as appropriate) and standardized difference. The standardized difference is the difference in means or proportions divided by the pooled standard deviation. Any covariable with a standardized difference greater than 0.2 in absolute value will be regarded as a potential confounder, and will be adjusted for when comparing Naloxegol and placebo groups on all the outcomes.

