#### E. Protocol

Patients must meet all inclusion and exclusion criteria to be eligible for the study. After eligibility is confirmed, patients will receive complete information about the study both verbally and in writing. Informed consent must be obtained from the patients prior to randomization and study-specific procedures.

Anesthetic management will follow pre-established clinical and institutional guidelines. Patients can be pre-medicated and will receive spinal or general anesthesia per institutional routine according to attending anesthesiologist discretion. Spinal anesthesia will include the standard monitoring for the given operation, and will occur after the electrocardiogram and monitoring equipment are placed on the patient. Prophylactic antibiotics will be given per surgical routine. During the induction of general anesthesia, indwelling urinary catheters will be inserted only in the patients with operation time exceeding 3 h or who required meticulous monitoring of the intraoperative fluid status. Intraoperative and postoperative fluid management will be left to discretion of the clinicians, who will be administrating them using institution standards.

Randomization (1:1) will be web-based and initiated prior to conclusion of surgery; allocation will thus be concealed from investigators. Randomization will be stratified based on chronic opioid use (if present) to ensure balance between treatment groups within chronic opioid users and nonusers. Chronic opioid use will be defined as opioid use for more than 30 consecutive days, at a daily dose of 15 mg or more of morphine or equivalent, within the 3 months before surgery. The treatment groups will be oral Naloxegol and placebo.

Naloxegol or placebo will be administered starting the first morning of surgery and continued for two postoperative days or until hospital discharge (whichever occurs first) with 25 mg (or equivalent size and shape of Placebo). The post-operative study drug doses will be given in the morning 1 hour before or 2 hours after the morning meal. Intraoperative and postoperative pain medications will be left to discretion of the anesthesiologist.

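### Adjustment covariates are picked by chance imbalance (standardized difference above 0.2) instead of being fixed in advance as prognostic, which costs some power and leaves the models undefined until the data are seen

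*Combined protocol and SAP*

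**What the plan says.** Section G, Data Analysis, compares the arms on baseline characteristics by standardized difference and then turns that comparison into a model-selection rule: "Any covariable with a standardized difference greater than 0.2 in absolute value will be regarded as a potential confounder". The flagged variables are adjusted for in the comparison of the arms on all outcomes. The primary analysis repeats the rule and adds one covariate that is always present: "Any imbalanced baseline characteristics and volume of residual urine in bladder prior to the procedure will be included as covariates in the model". The secondary analyses (two logistic regressions and the Quality of Recovery model) are adjusted for imbalanced baseline characteristics only.

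No section lists the candidate variables. Section E, Protocol, sets the allocation ("Randomization (1:1) will be web-based") and stratifies it by chronic opioid use, but the overall models do not name that stratum as a covariate. Section H, Sample Size Considerations, makes no allowance for covariate adjustment, as a loss or as a gain.

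**The concern.** In a randomised trial a baseline difference between arms is chance, so an imbalance threshold says nothing about whether a variable predicts the outcome. The rule has three consequences.

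- Variables unrelated to the outcome enter the model. Flagged variables are by construction correlated with arm, so they widen the standard error of the treatment effect unless they are prognostic.
- A prognostic variable is left out whenever it happens to be balanced, and the precision it would have given is lost.
- The model cannot be written down until treatment-coded data have been seen. For the logistic regressions this also affects interpretation, because an adjusted odds ratio is conditional on whichever covariates chance selected.

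At stake are some power and a fully defined primary model.

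**Working it through.** **Inputs from the plan.** Section H: "90% power at a 2-sided alpha level of 0.05 to detect an effect size of 0.4 or more", 62 per group, and "we assumed 4 measurements per patients with a correlation of 0.3 to be conservative for the sample size calculation". It then adds 12 patients for 10% loss, giving 136, or 68 per arm. With the full 10% lost, 0.9 × 68 = 61.2 per arm remain, so 62 is about the number the plan expects to analyse.

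**Reproducing the plan's figure.** The mean of 4 equally correlated scans has variance factor (1 + 3 × 0.3)/4 = 0.475. Then n = 2 × 0.475 × (1.960 + 1.282)² / 0.4² = 62.4 per arm, against 62 stated. Unadjusted power at 62 is 89.8%; at 68 it is 92.3%.

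**Chance of a flag.** The standardized difference has standard error √(2/n), and P(flag) = 2[1 − Φ(0.2/√(2/n))].

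- n = 62: standard error 0.180, P = 26.5%.
- n = 68: standard error 0.171, P = 24.4%.

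A given prognostic variable is therefore left out in about 74 to 76% of trials.

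**Number flagged.** Section F, Measurements, supports about 19 candidates (demographics, history items, tobacco, Apfel score, surgery type). The count is an assumption, so a range is shown.

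| Candidates | Expected flags, 62 per arm | 68 per arm |
|---|---|---|
| 10 | 2.7 | 2.4 |
| 19 | 5.0 | 4.6 |
| 25 | 6.6 | 6.1 |

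**Loss when the candidates are not prognostic.** At 62 per arm the mean squared standardized difference of a flagged variable is 2.80 × 2/62 = 0.090, where 2.80 is the mean of z² given |z| > 1.114. Each flag inflates the variance of the treatment effect by about 0.090/4 = 0.0226. With 5.04 flags the factor is 1 + 5.04 × 0.0226 = 1.114, and the standard error rises by a factor of 1.055. The unadjusted standard error is √(2 × 0.475/62) = 0.1238, which becomes 0.1306. Power is Φ(0.4/0.1306 − 1.96) = 86.5%. Simulation gives about 86% with 19 candidates, about 88% with 10 and about 85% with 25.

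**Comparison with a fixed set.** Simulated analysis of covariance on the patient mean, 62 per arm, effect 0.4, 4,000 trials per scenario (Monte Carlo error about 0.5 point). Assumptions: independent normal candidates, three of them prognostic with the joint R² shown, and pre-procedure residual volume not in the model. Unadjusted power is about 90%.

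| Joint R² | Rule, 19 candidates | Fixed three | Rule, 10 candidates | Fixed three |
|---|---|---|---|---|
| 0 | 86.3% | 89.0% | 87.6% | 88.7% |
| 0.1 | 87.5% | 92.4% | 89.2% | 91.8% |
| 0.2 | 88.4% | 94.4% | 89.7% | 93.7% |
| 0.3 | 90.6% | 96.7% | 91.7% | 95.9% |

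The gaps run from 1.1 to 6.1 points. A run with 20 candidates at R² 0.3 gave 90.2% against 97.1%, a gap of 6.9.

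**With pre-procedure residual volume in the model** (19 candidates, 62 per arm):

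| R² of volume | R² of the three others | Rule | Fixed set |
|---|---|---|---|
| 0.1 | 0 | 89.3% | 92.2% |
| 0.2 | 0 | 92.3% | 94.4% |
| 0.1 | 0.1 | 89.9% | 94.1% |
| 0.2 | 0.2 | 94.5% | 98.0% |

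In the rows with no other prognostic covariates, the fixed set is volume alone.

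**Type I error.** Under the rule it was 3.6 to 4.6%, the lower values arising when candidates are prognostic. The reason is that a prognostic variable that is left out is one whose imbalance is already small, yet its full variance stays in the residual, so the standard error is too large.

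**The case against.** The strongest defence is that the rule is objective and fixed in advance, does not inflate type I error, and answers the clinical reader who sees an imbalance in the baseline table. The primary model also always contains pre-procedure residual volume, a natural prognostic covariate. All of this stands. So does the remark that the comparison flatters the fixed set, which contains exactly the three prognostic variables; a real list would be less well chosen. Even so, three useless fixed covariates cost less (89.0%) than the rule does with 19 useless candidates (86.3%).

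A reader might infer four stronger things that the documents do not support.

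- *That 90% power is usually not delivered.* Unadjusted power at 62 per arm is already 89.8%, because 62.4 was taken as 62. The inference also needs equal correlation, about 20 weakly prognostic candidates, no gain from baseline volume and only 62 analysed per arm. If the data follow the autoregressive structure of the primary model with correlation 0.3, power is 95.0% before and about 92.5% after selection. At 68 per arm with 10 non-prognostic candidates, power falls below 90% in only 16% of randomisations.
- *That five variables enter every model.* Five is an expectation for an assumed 19 or so candidates.
- *That variables recorded after the first dose may be adjusted for.* The words on any covariable directly follow a sentence about baseline characteristics, and the primary and secondary analyses both speak of baseline characteristics.
- *That the primary model ignores prognosis altogether.* Residual volume is in it regardless of balance. Table 1, as it reads in the available text, marks no bladder scan before the PACU, so the source of that value should be confirmed; and the covariate does not extend to the secondary models.

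**Conclusion.** The point holds as a matter of efficiency and pre-specification, not of validity. At the plan's design point, with 10 to 20 assumed candidates, three of them prognostic with joint R² from 0 to 0.3, the rule loses up to about 4 points of power against no adjustment and about 1 to 7 points against a fixed prognostic set. The test becomes mildly conservative (about 4%) when candidates are prognostic. Whether power ends above or below 90% cannot be settled from the documents: it depends on how prognostic baseline volume is, on the true correlation pattern and on losses. The direction of the comparison is firmer, since the fixed set did better than the rule in every scenario run. The missing candidate list, the unnamed stratum and odds ratios conditional on a chance-selected set hold without any simulation. This is a cheap improvement.

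**What to change.** In section G and its primary and secondary analyses, stop using the 0.2 threshold to choose covariates. Keep standardized differences for the baseline table, and show the imbalance-adjusted model as a sensitivity analysis.

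Before unblinding, fix a short list of baseline covariates for all models: chronic opioid use, as the stratum, plus a few variables judged prognostic, such as age, sex, hip or knee, and primary or revision surgery. Keep pre-procedure residual volume in the primary model if it is measured, and say when. Use a shorter list for the logistic models if events are few.

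The cost is one paragraph of SAP text. The variables are already collected or known at scheduling, and no patients or procedures are added. The downside is a few degrees of freedom and a small loss of power if the chosen covariates turn out not to be prognostic (about 1 point for three in the simulations above).
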